how it worked/did not work; **iii)** their thoughts regarding our initial concepts; and **iv)** what they feel would help students use a mobile program. Interviews will employ a semi-structured open-ended approach, allowing for natural conversation with opportunities to explore unanticipated issues. Interviews will be recorded, transcribed, and coded.

The semi-structured interview is expected to last no more than 60 minutes. We will provide a \$100 gift card to the key informants for completion of this interview.

Compensation: Gift cards totaling up to \$120 (\$20-\$30 for each activity and the mini pilot) will be provided to adolescents for completion of Aim 1 activities. Gift cards of \$100 will also be provided to the key informants (school nurse and Vice Principal) and to the school nurses assisting with study activities (e.g., serving as the on-site point person for study recruitment, referring students requesting additional information regarding the study to research staff). There are two nurses at the high school, and we will provide a \$100 gift card per nurse.

See also Section #30, *Consent Process*.

Aim 2

We will recruit from 4-7 local high schools (that were not involved in Aim 1), selected for their high rates of racial/ethnic minorities and low SES status. Prior to recruitment, the study team will obtain IRB approval for the specific schools. To reduce the chances of imbalance across conditions, the schools will be matched based on percentage low income, percentage African American, and number of students, and divided into two sets of two. Within each set of two, we will randomly assign one school to each of the study conditions.

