We will recruit participants with approaches successfully used in our prior school-based studies. Recruitment packets containing an informational brochure, eligibility criteria, and adolescent assent/consent forms will be sent to all students. Flyers and posters will be placed in the school nurse's office and throughout the school. The study will be announced in health education classes and through school-wide class announcements. Recruitment materials will include the Research Coordinator's contact information. After flyers and posters are placed in the school nurse's office and throughout the school, and after the study has been announced in health education classes and through school-wide class announcements, interested adolescents will contact the Research Coordinator to indicate that they are interested in participating in the study. The Research Coordinator will then confirm that the adolescent's parents (or legal guardians) have not indicated that their child may not participate in the study and will schedule a meeting with the adolescent for the earliest possible date. Meetings with the Research Coordinator will take place in the privacy of the school nurse's office. The adolescent will not meet with the school nurse. Informed assent, or informed consent if the student is 18 years of age or older, will be explained such that students understand they have a right to refuse to participate, that their care in the school health clinic and their grades will not be affected by whether or not they decide to participate, and confidentiality will be emphasized. Eligible students will be enrolled and follow the protocol for their school condition. All students in each school will receive the same intervention. Flyers, posters, and announcements will be submitted to the IRB for review and approval prior to use in the study. All recruitment materials will be available in both English and Spanish.

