Aim 2A (Feasibility) Hypothesis H1: *We will be able to recruit 80 adolescents (20/school, 40 per study condition), and $\geq 85\%$ will be retained in each study condition at 6-month follow-up.* We will estimate recruitment rates, overall and per condition. Also, for each condition, we will model 6-month retention, using generalized estimating equation (GEE) logistic regression to account for within-school clustering and dependence over time.

Proposed Sample Size. As appropriate for a pilot study, we are estimating our power and sample size based on the feasibility hypothesis (H1). Because pilot studies do not provide meaningful estimates of effect sizes due to the imprecision inherent in small samples, we base our proposed sample size of 40 students per condition (20 per school) on obtaining precision in estimating condition-specific retention rates, providing important information for design and recruitment for the future R01 study. Based on our prior study of adolescent smoking cessation, estimated intra-school correlation=0.01, for a design effect due to within-school clustering of $1 + [0.01 \times (20 - 1)] = 1.19$, and an effective sample size per condition of $40/1.19 = 34$. Based on our prior studies in

adolescents in school settings, we anticipate at least 85% retention. Thus, a conservatively wide 95% exact CI for per-condition retention rate is (68.9%, 95.0%).

Aim 2B (Monitor V2V Engagement and Assess Program Satisfaction) As the trial progresses, we will monitor engagement overall and by participant subgroups (e.g. by gender, race, age) as a formative assessment. Then, as the trial ends, we will also use this information as a component of our summative evaluation. We anticipate that engagement will lead to positive changes in acceptability, and satisfaction, and cessation.

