Aim 2C (Cessation Outcomes) *Hypothesis H2: The intervention will be associated with greater cotinine-validated 7-day point prevalence vaping abstinence rates, lower time to first quit attempt, and less amount of e-cigarette use compared to control at 6-month follow-up.* We recognize that there is some controversy about estimating effect sizes from pilot studies. However, we are calculating effect sizes in our study to provide a range, recognizing that there might be uncertainties because of our small sample size. To estimate effect sizes for V2V intervention versus control, between-condition differences over time will be estimated for **cotinine-validated 7-day point prevalence abstinence** using GEE logistic regression with a random effect for school and fixed effects of condition, time point (baseline and 6 months), and their interaction. Missing data is handled using inverse probability weighting. By taking the repeated measurements into consideration, the GEE model is able to increase the power to test the difference in the outcome. COX regression modeling will be used to examine the intervention effect on **time to first quit attempt** adjusting for other covariates. **Amount of e-cigarette use** will be calculated as a reduction from baseline. We will model this reduction using negative binomial regression modeling if the variance of the distribution of risk reduction is over dispersed.

Other information important for the design of a future study includes standard deviations, as well as **preliminary assessment of possible mediators** such as engagement, behavioral capability, and self-efficacy. We will identify important mediators in exploratory analyses. Guided by the conceptual model based on SCT, we will assess effects of intervention on the mediator and the

effects of the mediator on the outcome, controlling for other mediators in the model, and confounders of the mediator-outcome relationship, and then estimate the proportion of the intervention effect explained. Given the limited sample size, conclusions from the mediation analyses will be limited and treated with caution, but modeling will allow us to explore the constructs of SCT and potential predictors towards a larger RCT.

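### Schools are randomised, but the models for time to first quit attempt and amount of use have no school component, so as written their intervals are too narrow (modestly so at an ICC of 0.01)

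*Combined protocol and SAP*

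**What the plan says.** Section 11 (Aim 2) matches schools into sets of two and states: "Within each set of two, we will randomly assign one school to each of the study conditions". It adds that "All students in each school will receive the same intervention". Condition is therefore constant within a school.

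Section 13 treats within-school correlation as real in three places:
- The retention model (Aim 2A) is a GEE logistic regression chosen to allow for clustering by school.
- The sample-size paragraph takes "estimated intra-school correlation=0.01" from a prior adolescent smoking cessation study and derives a design effect of 1.19 and an effective 34 students per condition.
- The abstinence model (Aim 2C) is a GEE logistic regression that names school as a random effect.

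The same Aim 2C paragraph then covers the two remaining H2 outcomes in a few sentences. For time to first quit attempt, "COX regression modeling will be used to examine the intervention effect on" that outcome, adjusted for further covariates that are not listed. Amount of use is taken as a reduction from baseline, and "We will model this reduction using negative binomial regression modeling if the variance of the distribution of risk reduction is over dispersed". Neither description mentions school, and no general statement elsewhere extends the school adjustment to these models.

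**The concern.** When whole schools are allocated, the variance of a treatment contrast includes between-school variation. A Cox or negative binomial model fitted to students as if they were independent leaves that part out, so any positive within-school correlation makes its standard errors too small.

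What is at stake is the width of the effect-size ranges. Aim 2C says that effect sizes are calculated to give a range, and the pilot is meant to inform a later R01. For two of the three H2 outcomes that range would look more precise than the design allows.

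Two features of the text might seem to supply the adjustment, and neither does:
- **Covariates in the Cox model.** School cannot enter as a fixed effect beside condition, because each school has only one condition and the two are aliased.
- **The negative binomial dispersion parameter.** It absorbs extra variation between students. It does not represent correlation among students of one school.

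**Working it through.** **Inputs**
- ICC 0.01; 20 students per school; 40 per condition (Section 13, Proposed Sample Size).
- 17 completers per school, 34 per condition, four schools (Section 25).
- Four to seven schools (Sections 6 and 11). Seven schools gives 80/7 = 11.4 enrolled per school.
- Assumed: two-sided 95% intervals for H2 (the plan states a level only for retention); ICC 0.01 applied to these two outcomes; ICC 0.02 and 0.05 as sensitivities that the documents do not give.

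**The plan's own figures reproduce**
- Design effect: 1 + 0.01 × (20 − 1) = 1.19.
- Effective n: 40/1.19 = 33.6, rounded to 34.
- Exact 95% interval for 29/34 (85.3%): 68.9% to 95.0%, as stated.

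**Effect of leaving school out**

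With DE = 1 + ICC × (m − 1), the naive standard error is 1/√DE of the correct one, and true coverage of a nominal 95% interval is 2Φ(1.96/√DE) − 1.

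| ICC | m per school | DE | √DE | SE too small by | Coverage |
|---|---|---|---|---|---|
| 0.01 | 20 | 1.19 | 1.091 | 8.3% | 92.8% |
| 0.01 | 17 | 1.16 | 1.077 | 7.1% | 93.1% |
| 0.01 | 11.4 (seven schools) | 1.10 | 1.051 | 4.8% | 93.8% |
| 0.02 (assumed) | 20 | 1.38 | 1.175 | 14.9% | 90.5% |
| 0.05 (assumed) | 20 | 1.95 | 1.396 | 28.4% | 84.0% |

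Worked for the first row: 1/1.091 = 0.917, so 8.3% too small; 1.96/1.091 = 1.797; 2Φ(1.797) − 1 = 0.928.

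**Check by simulation**

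Four schools of 20, two per condition, no true effect. A Cox model without school (1,500 runs) rejected in 7.3% of runs at ICC 0.01, against 5.1% at ICC 0 and 7.2% expected from the formula. Monte Carlo error is √(0.073 × 0.927/1500), about 0.7 percentage points. At ICC 0.05 it rejected in 16.3%, against 16.0% by formula. A normal outcome (20,000 runs) gave 7.6% at ICC 0.01 and 5.5% at ICC 0. The negative binomial model was not simulated; its figure rests on the formula.

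**Few schools**

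The table treats the ICC as known and uses a normal reference. If between-school variation must be estimated from the trial, four schools in two conditions leave 2 degrees of freedom and a critical value of 4.30. At DE 1.19 the interval is 4.30 × 1.091/1.96 = 2.39 times the naive width. With seven schools (5 degrees of freedom, critical value 2.57) it is 2.57 × 1.051/1.96 = 1.38 times. So with four schools the small number of clusters widens the interval far more than the design effect does.

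**The case against.** The strongest reply has four parts.

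1. **The plan is silent; it does not refuse.** A reader might infer that the sponsor has decided to ignore clustering for these outcomes. The documents do not support that: the descriptions are very short, and the plan handles school elsewhere. What stands is that an analyst who follows the text would fit models without school, since the neighbouring abstinence model names school and these do not.

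2. **The effect at ICC 0.01 is small, and that ICC is borrowed.** It comes from a prior study and is used for retention. The documents give no ICC for quit-attempt time or amount of use, and matching of schools and covariate adjustment may lower the residual correlation. All of this stands. The larger losses of coverage depend on ICCs that the documents do not give.

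3. **Effect sizes are secondary and already hedged.** Section 10 lists them as secondary. Section 13 warns of imprecision and sizes the trial on retention. As an illustration, assume 50 quit attempts split evenly by condition. The 95% limits then lie a factor exp(1.96 × 2/√50) = 1.74 either side of the hazard ratio, and exp(1.96 × 2 × 1.091/√50) = 1.83 after the 1.19 correction. That stands as a limit on importance. The plan's caveat, however, concerns small sample size and does not cover a variance that leaves out the randomised unit.

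4. **Abstinence is not a clean benchmark.** A reader might infer that the abstinence result is sound and only the other two need repair. The abstinence GEE has no stated small-cluster correction and faces the same four to seven schools. This stands, so the point is not argued from comparability with abstinence.

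**Conclusion.** The concern holds, at a modest size. As written, the Cox and negative binomial models omit the unit of randomisation, and nothing else in the documents supplies it. If ICC 0.01 is assumed to carry over, standard errors are about 5% to 8% too small across the school numbers in the plan, and nominal 95% intervals cover about 93% to 94%. Coverage falls further only under ICCs that are assumptions.

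Two stronger readings go too far. One is that the plan's own ICC shows a serious loss of coverage for these outcomes: the plan gives no ICC for them, and at 0.01 the loss is about two percentage points with four schools. The other is that multiplying variances by 1.19 settles the matter: that leaves the uncertainty from so few schools unaddressed.

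The consequence is confined to overstated precision in preliminary, secondary effect ranges. The change is worth making because it is cheap and the ranges are meant for planning the next trial.

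**What to change.** In Section 13, Aim 2C, state before analysis that the models for time to first quit attempt and amount of use both account for school:

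- Multiply each model's variance for the condition effect by 1 + ICC(m − 1) at the realised school size, using ICC 0.01, with 0.02 and 0.05 as sensitivities. Say how m is defined when school sizes differ.
- Label these intervals as conditional on the assumed ICC, and state that 0.01 comes from a prior study and is used in this plan for retention.
- Do not rely on an uncorrected sandwich variance with four to seven schools.
- Report an analysis of school-level summaries with a small-cluster t reference as a sensitivity, and say in advance that it will be much wider: about 2.4 times the naive width with four schools and 2 degrees of freedom.
- Acknowledge that the abstinence GEE faces the same few-cluster limit.

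The cost is analysis-plan wording and wider intervals on secondary estimates: about 9% wider under the inflation at 20 per school and ICC 0.01 (√1.19 = 1.091), and far wider in the school-level sensitivity analysis. Recruitment, sample size and the primary feasibility analysis do not change.

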10. STUDY ENDPOINTS*

The primary outcome for Aim 2 is the feasibility of the research protocols, including participant recruitment and retention. Secondary outcomes include: preliminary effect size estimates of the intervention on cotinine-validated 7-day point prevalence abstinence, time to first quit attempt, and amount of use; acceptability of and satisfaction with the intervention; system use and adoption of cessation supporting strategies; Social Cognitive Theory (SCT) constructs; and demographics and tobacco use.

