Enrollment: Interested adolescents whose parents (or legal guardians) have not opted out, or who are 18 or older, will meet with the Research Coordinator in the privacy of the high school nurse's office. The adolescent will not meet with the school nurse. After a brief screening, assent, or informed consent if the student is 18 years of age or older, will be explained such that students understand they have a right to refuse to participate, that their care in the school health clinic and their grades will not be affected by whether or not they decide to participate, and confidentiality will be emphasized. *See also #30, Consent Process.* The screening form will be submitted to the IRB for review and approval prior to use in the study.

Study Activities:

Trial: The control group will be provided written e-cigarette cessation materials. To the intervention group, we will provide access to the V2V toolkit, including access to peer coaches and peer messaging, detail how the peer messages and videos were pre-developed and set expectations for the response time from their peer coaches.

Baseline (study entry) and 6-month follow-up data will be collected from all enrolled Aim 2 participants in the privacy of the school nurse's office. Baseline and 6-month data collection forms will be submitted to the IRB for review and approval prior to use in the study; see Table 2 for a description of data to be collected. We have also included measures in the baseline and 6-month data collection forms to assess psychosocial factors (including the Perceived Stress Scale

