With participant permission, we will collect complete and accurate contact information from the student at baseline, including home address, phone, cell phone, email, and phone numbers of three contacts and best times and days to reach them to maximize retention. A contact sheet will be completed by the participant that will include the above information. Care will be taken to maintain the confidentiality of the student's participation; therefore all students will be asked to provide us with the individuals or contact information where they feel comfortable being contacted by study staff or where they feel assured that the confidentiality of their participation will be maintained. The other contacts provided by the student will not be informed of the student's vaping status. We have found in prior studies that cell phone numbers and e-mail addresses are particularly helpful in remaining in contact with this population. Tracking procedures will be implemented for any student who does not attend a scheduled study visit or who is not accessible by telephone or e-mail at the contact location provided. Attempts to locate students will be made mainly through the schools and by telephone calls to the contacts provided or directory assistance.

Table 2. Study Assessments, Measures and Data Collection Timing

Variable and Measure	Relevant Aim	Baseline	6-month follow-up
Recruitment: # screened and eligible, # and reasons for refusal	2A	•	
Retention: # of dropouts, reasons for dropping out	2A		•
Engagement (V2V only): # of completed responses to texting quizzes, peer videos viewed, peer coaching interactions	2B		*
Acceptability and satisfaction: Client Satisfaction Questionnaire (CSQ-8) semi-structured interview	2B		•
Cotinine-validated 7-day point prevalence abstinence: saliva samples collected from all; analyzed for those reporting 7-day abstinence; cut-off 11.4 ng/ml	2C		•
E-cigarette use frequency (past 7 and 30 day) and intensity (# days and amount vaped in past 7 and 30 day)	2C	•	•
THC/marijuana and other tobacco use frequency (past 7 and 30 day) and intensity (# days and amount vaped)		•	•
Social Cognitive Theory (SCT) constructs			
Self-efficacy, confidence to quit: Self-efficacy Questionnaire (SEQ-12)		•	•
Demographics and tobacco use			
Demographics: age, gender, socio-economic status, race/ethnicity, grade in school, academic performance		•	•
History of all tobacco use, past and recent quit attempts, cessation strategies used		•	

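### The planned proportion explained by self-efficacy rests on a score taken at the outcome visit, so it can be biased by reverse causation, and behavioral capability has no listed measure

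*Combined protocol and SAP*

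**What the plan says.** Section 13, Aim 2C, proposes an exploratory look at mediators "such as engagement, behavioral capability, and self-efficacy". For each it will estimate the effect of V2V on the mediator, then "effects of the mediator on the outcome, controlling for other mediators in the model", and finally "estimate the proportion of the intervention effect explained". The only stated reservation is the limited sample size.

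Section 11 fixes when things are measured: "Baseline (study entry) and 6-month follow-up data will be collected from all enrolled Aim 2 participants", and no visit is scheduled between the two. In Table 2 the block headed "Social Cognitive Theory (SCT) constructs" holds a single measure, "Self-efficacy, confidence to quit: Self-efficacy Questionnaire (SEQ-12", marked at baseline and 6 months. Abstinence (previous 7 days) and amount of use (previous 7 and 30 days) are assessed at the same 6-month visit. No row of Table 2 measures behavioral capability. The nearest item, on cessation strategies, sits among the demographic and tobacco-history rows and is marked at baseline only. Section 10 nevertheless lists among the secondary outcomes "system use and adoption of cessation supporting strategies".

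**The concern.** A mediator has to act before the outcome. Here the only post-baseline self-efficacy score is collected after the abstinence window, after the use windows, and after any first quit attempt made during follow-up. A student who has been abstinent for the past week may report more confidence for that reason. If V2V helps students quit by some other route, its arm will contain more quitters, the quitters will score higher on SEQ-12, and the model will credit self-efficacy with part of the effect.

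Section 13 says this work is meant to inform the design of a larger trial, so a false self-efficacy signal would have a reader. For behavioral capability the plan promises an estimate for which no score is scheduled.

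Engagement, the third named mediator, accrues during follow-up and is recorded in the V2V arm only. It raises different questions and is not part of this point.

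**Working it through.** **Plan's own figures.** The documents give no number for the mediation analysis, so there is none to reproduce. The only sample-size figures concern retention, and they do reproduce: design effect 1 + 0.01 × 19 = 1.19; 40/1.19 = 33.6, rounded to 34; exact 95% interval for 29/34 of 68.9% to 95.0%.

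**Does the planned adjustment help?** The plan will estimate mediator effects "controlling for other mediators in the model, and confounders of the mediator-outcome relationship". Such adjustment deals with common causes of mediator and outcome. It does not deal with a mediator that is partly an effect of the outcome.

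**Size under a simple model.** All inputs here are assumptions.
- Abstinence 10% (control) v 25% (V2V), equal arms, difference Δ = 0.15.
- 6-month self-efficacy M = d·Y + e, where Y is abstinence, e has SD 1, and d is the rise caused by quitting, in SD.
- Self-efficacy has no effect on Y, so the true proportion explained is 0.

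The steps are:
1. Average within-arm outcome variance: v = (0.10 × 0.90 + 0.25 × 0.75)/2 = (0.0900 + 0.1875)/2 = 0.139.
2. Effect of arm on mediator: dΔ.
3. Coefficient of mediator on outcome, given arm: d·v/(1 + d²v).
4. Product divided by Δ: apparent proportion explained = d²v/(1 + d²v).

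| d (SD) | d²v | apparent proportion explained |
|---|---|---|
| 0.3 | 0.012 | 1% |
| 0.5 | 0.035 | 3% |
| 1 | 0.139 | 12% |
| 1.5 | 0.312 | 24% |
| 2 | 0.555 | 36% |

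A simulation of 2,000,000 subjects gave 12.2%, 23.8% and 35.6% for the last three rows. The formula contains no sample size, so enrolling more students would not remove the bias.

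**Does adjusting for baseline SEQ-12 help?** A second simulation (400,000 subjects) adjusted for baseline self-efficacy and used assumed abstinence of 10 v 20%, 15 v 30% and 20 v 40%. The true value is again 0.

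| d (SD) | V2V has no effect of its own on self-efficacy | V2V raises self-efficacy by 0.3 SD |
|---|---|---|
| 0.3 | 1–2% | 14–17% |
| 0.5 | 4–6% | 25–29% |
| 0.8 | 10–15% | 42–45% |
| 1.0 | 15–21% | 53–58% |

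The bias remains after baseline adjustment, and it is larger if V2V raises confidence without that confidence leading to quitting. When self-efficacy was taken before any effect of quitting on it, the result was 0% in every scenario.

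**At the planned size.** With the 68 students expected at 6 months (Section 25), 15 v 30% abstinence, d = 0.5 and a 0.3 SD effect of V2V on self-efficacy, the median was 21%, with a 2.5 to 97.5 percentile range of −116% to 213%.

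**The case against.** The strongest reply is that little hangs on this analysis here. The primary outcome is feasibility. Section 13 calls the mediation work preliminary and exploratory, promises caution, and says that pilots do not yield meaningful effect sizes. At 68 students the proportion explained is so noisy that the bias is hard to see: in the simple model the 2.5 to 97.5 percentile range is about −59% to 86% at d = 1 and −72% to 147% at d = 2. This stands as a limit on importance. It does not justify the estimate, because the promised caution concerns sample size and the bias would persist in a large trial. A figure that is both imprecise and possibly biased is better not reported.

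A reader might infer something stronger: that the proportion explained is certainly and materially biased. The documents do not support that. They give no figure for how far quitting moves SEQ-12, and at 0.3 or 0.5 SD the simple model gives only 1% or 3%. A reader might also infer that the analysis is meant to pick the construct the next trial should target. Section 13 says only that it will explore the constructs and potential predictors.

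On behavioral capability, it can be said that the data forms are still to be submitted to the IRB, that the list of mediators is illustrative, that the content of the texting quizzes is not described, and that the interviews after the 6-month follow-up will touch on the conceptual model. So it would go too far to say that the trial can learn nothing about it. But none of these is a listed quantitative measure, and the quizzes appear in Table 2 only as a V2V-only engagement count.

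On cessation strategies, the row sits at a break in Table 2, so a lost 6-month mark cannot be ruled out. The same row covers quit attempts, which the Cox model needs after baseline. The Section 10 phrase could also refer to use of V2V's own tools. That part is therefore a matter to confirm and is separate from the mediation question.

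**Conclusion.** The point holds as a possible bias. The schedule gives no post-baseline self-efficacy score that precedes the outcome, and it lists no measure of behavioral capability, so the planned proportion explained cannot be read as mediation. With no true mediation and assumed abstinence of 10% v 25%, the apparent value runs from about 1% to 36% as the effect of quitting on SEQ-12 runs from 0.3 to 2 SD. It can be higher if V2V also raises confidence directly. These sizes rest on assumed abstinence rates and assumed shifts; the conclusion about timing rests on Table 2 alone. The feasibility outcome and the between-arm effect estimates are unaffected. This is worth correcting because the correction is cheap, not because the trial depends on it.

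**What to change.** 1. In Section 13, state that no proportion explained will be computed from the 6-month SEQ-12. Report the between-arm difference in 6-month SEQ-12 adjusted for baseline, and describe its association with abstinence as cross-sectional, with direction undetermined. Cost: wording only.
2. Drop behavioral capability from the mediation analysis unless a measure taken before the outcome is named. Cost: wording, unless a measure is added.
3. Separately, add the existing cessation-strategies item to the 6-month form, or confirm that it is already there, to serve the Section 10 outcome. It should not be used as a mediator: it would again be taken at the outcome visit, and using strategies can follow from trying to quit. Cost: one existing item on a form still subject to IRB review.
4. A mid-trial SEQ-12 in both arms is optional. It would need vaping status collected at the same time, because students who have already quit would carry the same bias. In the simple model, if 50% or 75% of eventual abstainers had quit by then, the false proportion is still 3% or 7% at 1 SD and 11% or 22% at 2 SD. It also adds a contact for controls, who otherwise receive written materials. Its possible effect on control-arm retention, part of the primary outcome, should be acknowledged, and the new form would need IRB review.
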